10.5. Safety Analysis

Analysis of safety data will be conducted on the Safety Population, which includes enrolled subjects who receive at least 1 dose of ibrutinib/placebo or rituximab. The baseline value is defined as the last value collected on or prior to the first dose date of ibrutinib/placebo or rituximab, whichever comes first.

The safety variables to be analyzed include exposure to ibrutinib/placebo or rituximab, AEs, deaths, clinical laboratory test results (hematology and chemistry), ECOG performance status score, physical examination, and vital sign measurements. In general, continuous variables will be summarized using descriptive statistics (n, mean, median, standard deviation, standard error and range). Categorical variables will be summarized using frequencies and percentages. No formal statistical testing is planned.

10.5.1. Adverse Events

Adverse event parameters to be evaluated are the type, incidence, and intensity of AEs; the relationship of AEs to study treatment; and the action taken with respect to study treatment due to AEs.

The verbatim terms used in the eCRF by investigators to identify AEs will be coded using the Medical Dictionary for Regulatory Activities (MedDRA).

The treatment-emergent period is defined as the period of time from the first dose of study treatment, until the earlier of:

- Thirty days following the last dose of ibrutinib/placebo or 30 days following the last dose of rituximab, whichever occurs later

OR

- The start date of a new anticancer therapy.

The Treatment-emergent adverse events (TEAEs) are those events that:

- Are not present prior to the treatment-emergent period and occur during the treatment-emergent period,
- The onset dates are missing, and end dates are during treatment-emergent period,
- Are considered related to study drug by the investigator regardless of the start dates of the events, or
- Are present prior to the treatment-emergent period but worsen in severity during the treatment-emergent period or are subsequently considered related to study drug by the investigator.

All TEAEs will be included in the analysis. For each AE, the number and percentage of subjects who experience at least one occurrence of the given event will be summarized. The number and percent of subjects with TEAEs will be summarized according to intensity (CTCAE, v4.03) and drug relationship, as well as categorized by system organ class and preferred term. Summaries, listings, datasets, or subject narratives may be provided, as appropriate, for those subjects who die, who discontinue treatment due to an AE, or who experience a severe AE or a SAE.

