5.1.2. Blinding

Blinded treatment will be used to reduce potential bias during data collection and evaluation of clinical endpoints. This is a double-blind study; therefore, subjects, investigators, and the Sponsor's study team members will remain blinded to treatment assignment. The investigator will not be provided with randomization codes.

Data that may potentially unblind the treatment assignment (i.e., study drug plasma concentrations) will be handled with special care to ensure that the integrity of the blind is maintained and the potential for bias is minimized. This may include making special provisions, such as segregating the data in question from view by the investigators, clinical team, or others as appropriate until the time of database lock and/or unblinding.

Under normal circumstances, the blind should not be broken. The blind should be broken only if specific emergency treatment/course of action would be dictated by knowing the treatment status of the subject. In such cases, the investigator may in an emergency determine the identity of the treatment by contacting the IXRS. It is recommended that the investigator contact the sponsor or its designee, if possible, to discuss the particular situation before breaking the blind. Telephone contact with the sponsor or its designee will be available 24 hours per day, 7 days per week. In the event the blind is broken, the sponsor must be informed as soon as possible. The date, time, and reason for the unblinding must be documented in the source documents. The documentation received from the IXRS indicating the code break must be retained with the subject's source documents in a secure manner. A subject whose treatment assignment has been unblinded may continue the study treatment if receiving clinical benefit and the subject should continue to return for scheduled study evaluations. The single-blind (i.e., subject remains blinded to treatment assignment) should be maintained provided the subject's safety is not compromised.

Subjects, investigators, and the sponsor's study team members will remain blinded to treatment assignment until the primary analysis is completed. Examples of personnel who may be unblinded during the study are:

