7.1.1.7. Adverse Events

The accepted regulatory definition for an adverse event (AE) is provided in Section [11.1](#). The occurrence of AEs at the time the ICF is signed until the first dose of study treatment should be entered in the medical history in the eCRF. Any medical occurrence after the first dose with study treatment until 30 days after the last dose of study treatment that meet the AE definition must be recorded as an AE in the eCRF. Laboratory abnormalities designated clinically

significant by the investigator will also be documented as AEs. Additional important requirements for AE and SAE reporting are explained in Section 11.4

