11.1. Definitions

11.1.1. Adverse Events

An AE is any untoward medical occurrence in a subject administered a pharmaceutical product and which does not necessarily have a causal relationship with this treatment. An AE can therefore be any unfavorable and unintended sign (including a clinically significant abnormal laboratory finding, for example), symptom, or disease temporally associated with the use of an investigational study treatment, whether or not considered related to the study treatment (ICH-E2A 1995).

For the purposes of this clinical study, AEs include events which are either new or represent detectable exacerbations of pre-existing conditions.

The term "disease progression" should not be reported as an AE term. As an example, "worsening of underlying disease" or the clinical diagnosis that is associated with disease progression should be reported.

Adverse events may include, but are not limited to:

- Subjective or objective symptoms provided by the subject and/or observed by the investigator or study staff including laboratory abnormalities of clinical significance.
- Any AEs experienced by the subject through the completion of final study procedures.
- AEs not previously observed in the subject that emerge during the protocol-specified AE reporting period, including signs or symptoms associated with the underlying disease that were not present before the AE reporting period
- Complications that occur as a result of protocol-mandated interventions (e.g., invasive procedures such as biopsies).

The following are NOT considered AEs:

- **Pre-existing condition:** A pre-existing condition (documented on the medical history eCRF) is not considered an AE unless the severity, frequency, or character of the event worsens during the study period.
- **Pre-planned or elective hospitalization:** A hospitalization planned before signing the ICF is not considered an SAE, but rather a therapeutic intervention. However, if during

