11.4.2. Adverse Event Reporting Period

All AEs whether serious or non-serious, will be documented from the time signed and dated ICF is obtained until 30 days following the last dose of study treatment. SAEs will be reported to the Sponsor Drug Safety via an SAE reporting form and will be recorded in the eCRF from the time of ICF signing. Non-serious AEs will be recorded in the source documents from the time of ICF signing and will be recorded in the eCRF from the first dose of study treatment.

Serious adverse events reported after 30 days following the last dose of study treatment should also be reported if considered related to study treatment. Resolution information after 30 days should be provided.

Progressive disease should NOT be reported as an event term, but instead symptoms/clinical signs of disease progression may be reported (See Section 11.1.1).

All AEs, regardless of seriousness, severity, or presumed relationship to study drug, must be recorded using medical terminology in the source document. All records will need to capture the details of the duration and the severity of each episode, the action taken with respect to the study drug, investigator's evaluation of its relationship to the study drug, and the event outcome. Whenever possible, diagnoses should be given when signs and symptoms are due to a common etiology (e.g., cough, runny nose, sneezing, sore throat, and head congestion should be reported as "upper respiratory infection"). Investigators must record in the CRF their opinion concerning the relationship of the AE to study therapy. All measures required for AE management must be recorded in the source document and reported according to Sponsor instructions.

All deaths should be reported with the primary cause of death as the AE term, as death is typically the outcome of the event, not the event itself. Autopsy and postmortem reports must be forwarded to the Sponsor, or designee, as outlined above, if allowed per local regulatory guidelines.

If a death occurs within 30 days after the last dose of study treatment, the death must be reported to the Sponsor as a SAE.

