## 5 SAFETY ASSESSMENTS

Safety data will be summarized by treatment for the safety population unless otherwise indicated. [Table 7](#) summarizes the safety analyses to be carried out. AEs will be coded in accordance with the Medical Dictionary for Regulatory Activities (MedDRA). Severity of AEs will be graded by the investigator according to the NCI Common Terminology Criteria for Adverse Events (NCI-CTCAE) v4.03.

The treatment-emergent period is defined as the period from the date of the first dose of study treatment up to 30 days after the date of the last dose of study treatment or the day before initiation of subsequent anti-cancer therapy, whichever comes first.

The treatment-emergent adverse events (TEAEs) are those events that occur or worsen during the treatment-emergent period or that are related to the study treatment. TEAEs or deaths related to COVID-19 infection will be summarized or listed separately. All laboratory values will be converted to and reported as international standard (SI) units. In general, only data from the central laboratory will be summarized and analyzed. When central lab values are missing and local lab values are available, local lab values will be used. Laboratory parameters will be graded using the NCI CTCAE v4.03. Unless otherwise specified, only baseline and post-baseline values collected during the treatment-emergent period will be included in the safety analysis.

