### 5.1 Exposure-Adjusted Incidence Rate

Exposure-adjusted incidence rate (EAIR) takes into account the patients' exposure time in quantifying the risk of an AE. For a given AE, EAIR is defined as the rate of the number of patients who experience at least one event over total time at risk for all subjects (Zhou, et. al.

2015; Jia, et. al. 2020). EAIR "adjusts for exposure" by accounting for the variability in patients time at risk as opposed to crude incidence rates, which divides the number of patients with events by the total number of patients. The time at risk is different for patients who have experienced the event and subjects who are event-free throughout the treatment-emergent period.

For patients with at least one event, the time at risk is the time from first dose date to the start date of the first event. The choice to restrict the time at risk to the onset of first event is due to EAIR's epidemiological origin and is based on the assumption that occurrences of multiple events are interdependent. Hence, for patients with events, the time at risk can be represented, in patient-years at risk, as:

$$(Start\ date\ of\ the\ first\ event - first\ dose\ date + 1)/365.25 \quad (equation\ 1)$$

For patients with no event, the time at risk is the time from the first dose date to the end of the treatment-emergent period which can be represented, in patient-years at risk, as:

$$(Last\ dose\ date + 30\ days - first\ dose\ date + 1)/365.25 \quad (equation\ 2)$$

The *total patient-years at risk* is the sum of the patient-years at risk for all subjects. For patients with events, patient-years at risk is calculated using equation 1, while for patients with no event, patient-years at risk is calculated using equation 2.

The *100 patient-years at risk* is the total patient-years at risk divided per 100 patients and can be interpreted as the average of length time (in years) to observe the first onset of AE if 100 patients were treated for 1 year.

For a given AE, the EAIR is represented as the number of patients with events per 100 patient-years at risk:

$$(Number\ of\ subjects\ with\ events/total\ patient-years\ at\ risk)*100,$$

or, equivalently

$$Number\ of\ subjects\ with\ events/100\ patient-years\ at\ risk$$

An equivalent interpretation of EAIR can be expressed as the "average number of patients experiencing the event of interest if 100 patients were treated for 1 year".

EAIRs may be summarized for all TEAEs, fatal TEAEs, and serious TEAEs.

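### The exposure-adjusted incidence rate in SAP 5.1 can count related events that start outside the treatment-emergent period, while event-free subjects stop contributing time when that period ends

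*Protocol*

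**What the plan says.** Protocol 10.5.1 defines a treatment-emergent period ending 30 days after the later of the last ibrutinib/placebo or rituximab dose, or at new anticancer therapy if that is earlier. It then admits as TEAEs events that "Are considered related to study drug by the investigator regardless of the start dates of the events". SAP 5 defines TEAEs as "those events that occur or worsen during the treatment-emergent period or that are related to the study treatment". The SAP's introduction gives its methods precedence over the protocol, but on this limb the two agree.

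Routine collection is narrower. Protocol 7.1.1.7 covers "Any medical occurrence after the first dose with study treatment until 30 days after the last dose of study treatment". Beyond that, 11.4.2 states: "Serious adverse events reported after 30 days following the last dose of study treatment should also be reported if considered related to study treatment". New malignancies are also collected through survival follow-up (11.4.5), without a relatedness condition and on their own eCRF.

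SAP 5.1 defines the EAIR as subjects with at least one event per 100 patient-years at risk. For a subject with an event, equation 1 runs from first dose to the start of the first event, with no cap. For a subject without one, "the time at risk is the time from the first dose date to the end of the treatment-emergent period", and equation 2 implements this as last dose plus 30 days. EAIRs may be produced for all, fatal and serious TEAEs.

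**The concern.** A rate is interpretable when a subject can add an event only during time that would also be counted had no event occurred. Here a subject can add an event well after last dose plus 30 days. Other subjects in the same off-treatment follow-up, for whom a related serious adverse event (SAE) would still be reported, add no time beyond that point. The late entries are also selected, because outside the window they depend on seriousness and on the investigator's judgement of relatedness.

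SAP 5.1 does not settle the case itself. It contrasts subjects who had the event with subjects who had none during the treatment-emergent period. A subject whose only event is a late related SAE fits both descriptions, so both equations apply. SAP 5.2 points the other way: its yearly prevalence tables carry ongoing events forward only while the subject is within 30 days of the last ibrutinib/placebo dose.

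At stake is the readability of a safety rate. AE frequency, severity, seriousness and relatedness form a listed secondary endpoint, and fatal and serious TEAEs are named for the EAIR.

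**Working it through.** The plan gives no EAIR to reproduce, so the check applies its two equations to single subjects and then to an arm under stated assumptions.

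**Single subject (first dose day 1, last dose day 365)**

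- Event-free, equation 2: (365 + 30)/365.25 = 1.081 patient-years (PY), however long the subject is followed.
- Only event is a related SAE 180 days after last dose, equation 1: (365 + 180)/365.25 = 1.492 PY and one event.
- The same at 365 days after last dose: 730/365.25 = 1.999 PY and one event.
- Confined to the treatment-emergent period, the two late cases would each give 1.081 PY and no event.

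**Edges of the equations**

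- An event called related that starts 1 day before first dose: (-1 + 1)/365.25 = 0 PY. Starting 10 days before: (-10 + 1)/365.25 = -0.025 PY. The limb does not exclude this, and SAEs enter the eCRF from consent (11.4.2).
- SAP 5 ends the period on the day before subsequent anti-cancer therapy if that comes first; equation 2 does not. If therapy starts the day after last dose, equation 2 credits 30 days too many, 30/365.25 = 0.082 PY.

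**Arm level (all inputs assumed; the documents give none of these rates)**

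Let p be the proportion with an in-window first event (on average at mid-window), q the proportion whose first event is late and related, W the window in years, and D the delay after the window in years. Arm size cancels; 0.75 x 445, or about 334, was used.

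- Confined to the window: 100p / [pW/2 + (1 - p)W]
- As written: 100(p + q) / [pW/2 + (1 - p)W + qD]

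With W = 2, D = 0.25, q = 0.01:

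| Summary | p | Confined | As written | Change |
|---|---|---|---|---|
| Fatal | 0.05 | 5/1.95 = 2.56 | 6/1.9525 = 3.07 | +19.8% |
| Serious | 0.40 | 40/1.60 = 25.00 | 41/1.6025 = 25.59 | +2.3% |
| Any | 0.98 | 98/1.02 = 96.08 | 99/1.0225 = 96.82 | +0.8% |

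Over W from 1 to 3 years, q from 1% to 2% and D from 0.25 to 1 year, the change is 19-40% for fatal, 1-5% for serious and about -2% to +2% for any TEAE. For rare events it is close to q/p (0.01/0.05 = 20%; 0.02/0.05 = 40%).

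**Between arms (fatal, p = 0.05 in both, W = 2, D = 0.5, confined ratio 1.00)**

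- q of 1% in both arms: the ratio stays 1.00.
- q of 2% in Arm A and 1% in Arm B: (7/1.96)/(6/1.955) = 1.16.
- q of 1% in Arm A and 2% in Arm B: (6/1.955)/(7/1.96) = 0.86.

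**The case against.** The strongest reply is that little depends on this. Protocol 10.5 plans no formal safety testing, EAIRs are optional, and only first events count. The infusion-related reaction rate, which is in the testing hierarchy, has its own definition tied to the infusion day. That bounds the consequence but does not repair the formula, and the summaries named for the EAIR include the sparse ones that move most.

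A second reply is that keeping late related events guards against under-reporting delayed toxicity. For TEAE counts that is a defensible choice of presentation. A rate also needs a matching denominator.

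A third is that SAP 5 closes by limiting safety values to the treatment-emergent period. That sentence follows the laboratory text and speaks of baseline and post-baseline values. If it did cover AEs, it would contradict the relatedness limb in the same paragraph.

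Several stronger readings are tempting but not supported:

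- **Attribution becomes unblinded after day 30.** Investigators "will remain blinded to treatment assignment until the primary analysis is completed" (SAP 1.6.1 specifies the PFS primary analysis). Apart from individual code breaks, unblinded attribution could arise only after that analysis. The planned gap to the final OS analysis is 91 - 77 = 14 months.
- **Late events accrue mainly to Arm A.** The SAP's introduction defines study treatment to include rituximab, which both arms are scheduled to receive for up to 16 doses. Arm B can therefore contribute late related events, and no late related-event rates are given for either arm.
- **Protocol 11.1.1 contradicts the collection window.** Its line, "Any AEs experienced by the subject through the completion of final study procedures", sits in a list of what AEs may include. It is definitional; 7.1.1.7, 11.4.2 and Appendix A agree on 30 days.
- **Undated events are mishandled.** The limb "The onset dates are missing, and end dates are during treatment-emergent period" appears only in the protocol; the governing SAP definition does not carry it.

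**Conclusion.** The EAIR in SAP 5.1 is wrong as written. Through the relatedness limb its numerator can extend beyond the treatment-emergent period, equation 1 follows it without a cap, and equation 2 stops event-free subjects at last dose plus 30 days. Two smaller faults go with it: equation 2 omits the SAP's own cut-off at subsequent therapy, and an event called related that starts more than a day before first dose gives negative time at risk.

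The size is negligible for any TEAE, small for serious TEAEs taken together, and potentially material only for fatal or rare serious TEAEs. The percentages rest entirely on the assumed in-window proportions, late-event proportions, windows and delays. The mismatch itself rests on the text alone. No between-arm bias is shown in either direction.

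**What to change.** In SAP 5.1:

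- Count in the EAIR numerator only first events with onset or worsening inside the treatment-emergent period of SAP 5, and run equation 1 to that date.
- Treat a subject whose only event is later as event-free, with time ending at the end of the period.
- End equation 2 at the earlier of last dose plus 30 days and the day before subsequent anti-cancer therapy.

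Report related SAEs with onset after the period in a separate by-arm table, flagged as before or after unblinding. Whether they also stay in the main TEAE counts can be left to the sponsor as a matter of presentation.

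The cost is a short edit to SAP 5.1 and one table. The small downside is that late related SAEs leave the EAIR and appear in their own table; no data are lost.

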10.5.2. Clinical Laboratory Tests

Laboratory tests will be summarized separately for hematology and serum chemistry. Local laboratory results will be standardized using the International System SI unit. Selected hematologic and chemistry laboratory parameters are detailed in Section 7. All laboratory values will be graded using the NCI CTCAE v4.03. The worst toxicity grade during the study will be tabulated.

A summary of the shifts in selected laboratory hematology and serum chemistry parameters from baseline to the worst toxicity grade during the study will be provided. The worst toxicity grade during the study will be tabulated.

10.6. Analysis Methods for Selected Exploratory Endpoints

10.6.1. Pharmacokinetic Analysis

The plasma concentration data for ibrutinib and PCI-45227 will be summarized using descriptive statistics at each time-point. Population PK analysis of plasma concentration-time data of ibrutinib will be performed using nonlinear mixed-effects modeling. Data may be combined with data from other studies to support a relevant population PK model. Available subject characteristics (e.g., demographics, laboratory variables, genotypes, etc.) will be tested as potential covariates affecting PK parameters. Details will be given in a population PK analysis plan and the results of the population PK analysis will be presented in a separate report.

Ibrutinib PK data in this study will be compared to observed/reported concentration data for ibrutinib and/or population PK models to explore the potential for a pharmacokinetic interaction

between ibrutinib in combination use with rituximab. Rituximab concentration data in this study will be compared between two arms with and without ibrutinib to explore the potential for a pharmacokinetic interaction between rituximab in combination use with ibrutinib.

For the drug combination of ibrutinib and rituximab, model-derived exposure parameters (PK parameters) may be used to explore PK/PD correlation between the exposure of ibrutinib and its active metabolites with relevant clinical or biomarker information to assess effectiveness and toxicity.

